### Clinical study description

The clinical study ACTIVA 2 is a pragmatic, interventional, nonrandomized, single-arm, single-center.

The investigation is for research purposes (for publication in scientific journals), non-commercial, and for clinical development of the ACTIVA control software.

The primary outcome measure is the depth of hypnosis adequacy. It is assessed by means of the percentage of the anesthesia maintenance duration in which the BIS is kept inside the recommended range from 40 to 60. The percentage of the anesthesia maintenance duration in which the BIS is kept below 40 is also specified. Maintenance duration is the period of time that goes from the end of anesthesia induction to the point at which the automatic control is turned off at the conclusion of surgery. The end of anesthesia induction is defined as the time instant when the BIS drops below 40 for the first time and remains there for the subsequent 30 seconds.

The secondary outcomes measures are:

- Number and types of dysfunctions of the ACTIVA automatic infusion system.
- Level of satisfaction of the experimenter. It is expressed on a scale from 0 to 10 regarding the ease of use of the ACTIVA software and its infusion system, the induction phase of anesthesia and the maintenance phase of anesthesia.
- Effect of drugs delivery on heart rate. It is assessed by means of the percentage of the anesthesia maintenance duration in which the heart rate (HR) is kept inside the range from 50 to 100 beats per minute. The percentage of the anesthesia maintenance duration in which the HR is kept below 50 is also specified.
- Effect of drugs delivery on mean blood pressure. It is assessed by means of the percentage of the anesthesia maintenance duration in which the non-invasively measured mean blood pressure (MBP) is kept inside the range from 65 to 110 mmHg. The percentage of the anesthesia maintenance duration in which the MBP is kept below 65 is also specified.
- Postoperative heart rate stability. It is assessed by measuring the HR in bpm.
- Postoperative Mean Blood Pressure Stability. It is assessed by non-invasive measuring of the mean blood pressure in mmHg.

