## Information related to the clinical investigation

### Clinical study objectives

The primary objective of the clinical investigation is to investigate the clinical performances obtainable by the control system under study in terms of depth of hypnosis adequacy.

The secondary objective is to evaluate the reliability, safety and applicability of the control system under study and to carry out the clinical evaluation of the automatic control system during the induction, maintenance and recovery of general intravenous anesthesia.

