## Measured variables

For each patient enrolled in the study, the following variables will be collected:

- Age.
- Gender.
- Weight
- Height
- Type of surgical procedure
- Anesthesiological risk assessment according to the American Society of Anesthesiologists (ASA) physical status classification system.
- PONV risk assessment according to the Apfel simplified risk score.

These data are collected by the principal investigator at patient arrival in the operating room, before surgery and they are noted on the patient's anesthesiology clinical record form.

The following variables are automatically collected by the ACTIVA software, they are recorded in real-time every second and stored on a ".csv" file:

- HR.
- Peripheral oxygen saturation.
- MBP.
- BIS.
- BIS signal quality index (SQI).
- Burst suppression ratio.
- Infusion rates of propofol and remifentanil.

The following data are collected by the principal investigator after surgery and noted on the patient's anesthesiology clinical record form.

- System dysfunctions.
- Level of satisfaction of the experimenter.
- HR.
- MBP.
- Postoperative sedation.

---

 Burst suppression is defined as a period on the EEG trace characterized by attenuated or suppressed signal (<10 mV) alternating with brief periods of cortical activity, precisely termed 'bursts.' More than 50% of this period is dominated by attenuated/suppressed activity. This effect may sometimes be intentionally induced, for example, during neuroanesthesia, as a protective measure against cerebral ischemia, as it coincides with a reduction in cerebral metabolism. However, it is important to consider that it is also associated with a higher incidence of postoperative delirium.

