## Statistical analysis

The statistical analysis consists in the descriptive statistics of the collected data.

Synthetic statistical data are calculated for all study variables.

For quantitative data mean and standard deviation, or median and interquartile range are calculated according to data distribution. Data normality is checked by using the Shapiro-Wilk test.

Categorical variables are synthesized by using patient count and percentage of patients belonging to each category.

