### Selection bias at the time of analysis.

The clinical trial requires that closed-loop anesthesia be practiced from the initiation of the ACTIVA software until the end of the surgical procedure. However, it may happen that:

- The primary experimenter decides to interrupt the software; in this case, it must be recorded in the report file.
- The software or its components (monitors, infusion pumps) may cease to function correctly; in this case, the system is halted and switches to manual mode or requires the experimenter's intervention. The experimenter must record the event in the report file. If the above occurs, it is the responsibility of the experimenter to assess the possibility of including in the data analysis what has been collected up to the moment of system interruption.

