¹ Burst suppression is defined as a period on the electroencephalogram trace characterized by attenuated or suppressed signal (<10 mV) alternating with brief periods of cortical activity, precisely termed 'bursts.' More than 50% of this period is dominated by attenuated/suppressed activity. This effect may sometimes be intentionally induced, for example, during neuroanesthesia, as a protective measure against cerebral ischemia, as it coincides with a reduction in cerebral metabolism. However, it is important to consider that it is also associated with a higher incidence of postoperative delirium.

Statistical Analysis Plan

Automatic Control of Total Intravenous Anesthesia: Closed-loop Delivery of Propofol and Remifentanil Using Bispectral Index as Feedback Variable.

Acronym: ACTIVA 2. Id code: NP-2861. NCT number: NCT04432974.

The following data are collected by the principal investigator after surgery and noted on the patient's anesthesiology clinical record form.

- System dysfunctions.
- Level of satisfaction of the experimenter.
- HR.
- MBP.
- Postoperative sedation.
- PONV.
- Postoperative analgesia.

Descriptive statistics will be performed on all study variables.

Quantitative data will be presented as mean (SD) or median (IQR) according to their distribution. Normality of the data will be tested using a Shapiro-Wilk test. Categorical data will be presented as frequency (proportion).

Data management

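### Reliability is measured by the number and types of dysfunctions, with no hours of automatic control and no interval, so the result cannot say what failure rate it excludes

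*Protocol*

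**What the plan says.** The Protocol (Clinical study objectives) states: "The secondary objective is to evaluate the reliability, safety and applicability of the control system under study". The outcome that serves reliability most directly is listed first among the secondary outcomes in the Protocol (Clinical study description), and again in the SAP (Outcomes): "Number and types of dysfunctions of the ACTIVA automatic infusion system". The experimenter's satisfaction score also bears on applicability, but it is subjective.

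On analysis, the Protocol (Statistical analysis) says: "The statistical analysis consists in the descriptive statistics of the collected data". For categorical data: "Categorical variables are synthesized by using patient count and percentage of patients belonging to each category". The SAP (Analyses) has the equivalent rule of frequency and proportion. Neither document mentions a rate over time or a confidence interval for dysfunctions.

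On time, the monitoring and infusion variables are "recorded in real-time every second and stored on a" .csv file (Protocol, Measured variables), but duration of automatic control is not a listed variable. The only interval defined is maintenance, which runs "from the end of anesthesia induction to the point at which the automatic control is turned off" when surgery ends. It is used for the BIS, heart rate and blood pressure percentages, and it leaves out induction.

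**The concern.** A failure count is hard to interpret without the exposure that produced it. Exposure will differ between patients here. Any type of procedure in the room is eligible (Protocol, Participation criteria). Control can also end early, either at the experimenter's discretion or because a component fails, in which case "the system is halted and switches to manual mode or requires the experimenter's intervention" (Protocol, Selection bias at the time of analysis).

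Three uses of the result are affected:

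- **Adequacy of testing.** The Protocol (Number of patients enrolled) asserts that 139 patients are enough to test reliability, but states no target failure rate or exposure. A low or zero count with no interval does not let a reader judge that.
- **Software changes.** The study may be interrupted until a reliable version exists (Protocol, Factors that may compromise the outcome), and the device may go back to the manufacturer for updates (Device Responsibilities). Counts before and after a change mean little without the hours behind each.
- **Other systems.** Comparing failure frequency with another closed-loop device needs a common unit.

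**Working it through.** **The plan's own figure.** The documents give no failure rate or exposure time to reproduce. The only computed figure is the sample size. With p = 0.90 and a 95% Wald interval of half-width 0.05, n = 1.96² × 0.90 × 0.10 / 0.05² = 138.3, so 139. It matches when the stated 10% margin is read as the full width of the interval; read as a half-width, the formula gives 34.6, so 35. The point below does not depend on this; it uses only 139 as the number of sessions.

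**What the plan could report as written.** Dysfunctions are noted on each patient's record form, so the categorical rule can yield a percentage of patients. If 10 patients had one dysfunction each, that is 10/139 = 7.2%. The exact binomial 95% CI would be 3.5% to 12.8%, but the plan does not call for it. For 0/139 the exact upper limit is 2.6%. These figures stay the same however long the sessions last.

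**What hours add.** *Assumption:* mean automatic-control time h of 1, 2 or 4 hours per session, because the documents give no duration. The event counts of 10 and 0 are also assumed.

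- Total hours: T = 139 × h.
- Rate per 100 h: 100 × x / T, where x is the number of dysfunctions.
- Exact Poisson 95% limits for the count: lower = χ²(0.025; 2x) / 2, upper = χ²(0.975; 2x + 2) / 2. For x = 10 these are 4.795 and 18.390. For x = 0 the upper limit is 3.689.
- Limits for the rate: 100 × count limit / T.

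| h per session | T (hours) | 10 dysfunctions: rate per 100 h (95% CI) | 0 dysfunctions: upper limit per 100 h |
|---|---|---|---|
| 1 | 139 | 7.19 (3.45 to 13.23) | 2.65 |
| 2 | 278 | 3.60 (1.72 to 6.62) | 1.33 |
| 4 | 556 | 1.80 (0.86 to 3.31) | 0.66 |

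The rates differ four-fold between the first and last rows only because 4 h is four times 1 h. The table shows what the reported number leaves open; it does not estimate this trial's failure rate.

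**Who is counted.** Three Protocol sections bear on the numerator and do not agree:

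- *Subject Enrollment Count* treats patients who stop while the software is running as fully enrolled and has all their data analysed.
- *Selection bias at the time of analysis* leaves it to the experimenter whether data up to an interruption can be used.
- *Deviations from the clinical evaluation plan* removes patients who do not complete because of software problems from the secondary outcomes, which include the dysfunction count.

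Under the third rule, the patients with the most serious failures would leave the measure of failure.

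**The case against.** The strongest reply is that this is a descriptive secondary outcome in a single-arm study. It was not used for sizing, and no comparison of dysfunction rates is planned. No data are lost: hours can be recovered from the one-second files. All cases come from one plastic-surgery operating room, which may limit the spread of durations. All of this is fair, and it makes the point a reporting gap that does not touch the primary outcome.

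Several stronger readings are tempting, and the documents do not support them:

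- *That the plan reports a bare number with no denominator, so several events in one patient look like one event in each of several patients.* Dysfunctions are recorded per patient and the categorical rule allows a patient percentage. What is missing is a stated measure of patients with at least one dysfunction, the hours, and an interval.
- *That only hours will do.* The software cannot begin infusing if devices or connections fail (Protocol, Interaction between the ACTIVA software and the experimenter). Start-up failures therefore scale with sessions, and a per-session proportion suits them.
- *That cutting sessions short always flatters the result.* A malfunction that halts a session must still be recorded. The argument applies only to discretionary stops without a malfunction, or where the exclusion under Deviations is applied.

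The objection also holds against a simple remedy. A Poisson interval assumes independent events at a constant rate, and is too narrow if events cluster within patients.

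**Conclusion.** The point holds as a gap in outcome definition and reporting. Reliability is a stated objective, yet the plan would give at most a count, a list of types and a percentage of patients, with no exposure time and no interval.

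The size for this trial cannot be known from the documents. Under the assumed 1 to 4 h per session, the same 10 dysfunctions mean 7.2 or 1.8 per 100 h, and zero dysfunctions exclude rates above 2.7 or 0.7 per 100 h. A reader might take the four-fold spread as evidence of a problem in these data; it reflects only the assumed durations. The Poisson limits assume independent events. The sample size and the primary outcome are unaffected.

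**What to change.** In the SAP (Outcomes and Analyses), keep the number and types of dysfunctions and add:

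1. The number and proportion of patients with at least one dysfunction, with an exact binomial 95% CI. Report start-up failures per session.
2. Total hours of automatic control, and dysfunctions per 100 h, overall and by type, with an exact Poisson 95% CI. If any patient has more than one event, use a patient-level bootstrap or a robust interval.
3. A definition of exposure: from the start of automatic control to its stop or switch to manual, taken from the .csv and report files. It should not run to the end of the file, because recording continues until the patient wakes (Protocol, Enrollment procedure).
4. A stated analysis set for this outcome: every patient in whom the system was started or start-up was attempted. Reconcile Subject Enrollment Count, Selection bias at the time of analysis, and Deviations from the clinical evaluation plan, so that patients who stop because of software problems are not dropped from it.

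The cost is SAP wording and one extra table from data already collected. The interval will be wide if events are few.

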### Clinical Investigation Plan

Automatic Control of Total Intravenous Anesthesia: Closed-loop Delivery of Propofol and Remifentanil Using Bispectral Index as Feedback Variable.

Acronym: ACTIVA 2. Id code: NP-2861. NCT number: NCT04432974.

	supervision of the investigator. The anesthetic drugs used are those recommended for total intravenous general anesthesia: propofol and remifentanil.
Risk/Benefit assessment	The major risk of the study is the malfunction of the control program, which would require a switch to manual control (the traditional approach to general anesthesia). There is constant supervision by the investigator, and the control software and infusion pumps have adequate alarm systems in case of malfunction. The ACTIVA software has been developed and subjected to simulations to ensure the minimization of risks related to the infusion system. The benefits for enrolled patients are related to the increased stability of anesthesia during induction and maintenance phases. Constant closed-loop control of infusions and the level of hypnosis could lead to a superior quality of the postoperative recovery. The closed-loop system could also reduce the hemodynamic impact that general anesthesia has on the patient, particularly by reducing hypotension.
Study duration	One year, considering an average enrollment of three patients per week.
Follow up	Each patient is reassessed at 6 hours and at 24 hours after awakening from total intravenous anesthesia.

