### Clinical Investigation Plan

Automatic Control of Total Intravenous Anesthesia: Closed-loop Delivery of Propofol and Remifentanil Using Bispectral Index as Feedback Variable.

Acronym: ACTIVA 2. Id code: NP-2861. NCT number: NCT04432974.

The anesthesiologist has a role that includes controlling and regulating various parameters and vital functions of the patient through the administration of drugs, fluids, and the adjustment of hypnosis, analgesia, neuromuscular blockade, temperature, metabolic state, ventilation, and hemodynamics. The complexity of these tasks is further compounded by the intra- and inter-individual variability of patients and anesthesiologists themselves. These factors lead to a range of effects: they make human control suboptimal, influence the outcome of the anesthetic procedure, and significantly limit the ability to establish strict standards of care.

A step forward in this direction can be provided by so-called “closed-loop” control systems. These are automatic control systems that operate on the principle of feedback, and their key elements consist of a measuring device (sensor), a control device (controller), and an actuating device (effector). The sensor measures the controlled variable, which is representative of the desired behavior of the system (system output). This measurement is compared with the desired value (set-point), and the difference between these two values (error) is used by the controller to calculate the value of the control variable (system input).

In the case of TIVA, the system under control is identified as the patient, the effector is represented by the means through which drugs are administered (for example, infusion pumps), the manipulated variable is represented by the infusion rate of drugs, the controlled variable can be a parameter that quantifies the desired effect directly or indirectly, and the sensor is the respective monitoring system. For example, the controlled variable can be represented by the depth of hypnosis measured with a brain activity monitoring system based on the measurement and processing of the patient's electroencephalogram (EEG).

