## Concomitant medications and medical treatments

The ACTIVA control system is used during intravenous general anesthesia for elective surgical procedures. During the operation of the ACTIVA software, the surgical procedure is ongoing. However, the ACTIVA control system does not interfere with the surgical procedure in any way.

For clinical needs, medications that interact with propofol and remifentanil may be administered. However, with the ACTIVA control system, there are no additional risks compared to the normal clinical practice of TIVA regarding these interactions. However, these medications could alter the interpretation of the outcome measures used to evaluate the secondary objective of the study. For this reason, the experimenter records the use of such medications in the notes section of the GUI so that this event is documented in the report file and can be considered during the analysis of the results.

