#### **Factors that may compromise the outcome and interpretation of the results**

It is possible that the use of other sedative drugs in addition to propofol and remifentanil may affect the secondary objectives of the study, both in a negative and positive sense. The experimenter enters the use of such drugs in the notes of the ACTIVA software GUI, and this event remains recorded in the report file and will be considered during the analysis of the results.

It is possible that the experimenter may forget to enter events, drugs, or assessments relevant to the primary and secondary objectives in the notes of the ACTIVA software GUI. To minimize this risk, experimenters are trained according to the user manual and the current clinical protocol.

It is possible that the ACTIVA software, despite the pre-clinical development process and numerous simulations, does not meet reliability and safety criteria. In such a case, the study

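### The HR and MBP outcomes are named as effects of drug delivery, but they describe the controller together with the anesthesiologist's hemodynamic treatment, which neither document lists as a variable

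*Protocol*

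**What the plan says.** **Outcomes.** The protocol (Clinical study description) names and defines the pressure outcome thus: "Effect of drugs delivery on mean blood pressure. It is assessed by means of the percentage of the anesthesia maintenance duration" with MBP from 65 to 110 mmHg. It adds: "The percentage of the anesthesia maintenance duration in which the MBP is kept below 65 is also specified". The heart-rate outcome has the same form, "Effect of drugs delivery on heart rate. It is assessed by means of the percentage of the anesthesia maintenance duration" with HR from 50 to 100 bpm, plus the time below 50. The SAP (Outcomes) repeats both definitions.

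**Variables.** The only intraoperative drug data listed in the protocol (Measured variables) are "Infusion rates of propofol and remifentanil". The list in the SAP (Analyses) is the same. Neither includes a drug or fluid given to change pressure or heart rate.

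**Other drugs.** The protocol (Concomitant medications and medical treatments) says that "medications that interact with propofol and remifentanil may be administered". It has their use written in the notes field of the software because they may change how the secondary measures should be read. The section on factors that may compromise the results says that "the use of other sedative drugs in addition to propofol and remifentanil may affect the secondary objectives". Its next paragraph accepts that the experimenter may forget to note events, drugs or assessments that bear on either objective, and relies on training to limit this.

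**Who acts on hemodynamics.** The study rationale describes the anesthesiologist's role as "controlling and regulating various parameters and vital functions of the patient through the administration of drugs, fluids" and other means, and it names hemodynamics among the things regulated. The device description and the section on instrument-phenomenon interaction say that the software sets infusion rates from the BIS. The Summary says of the closed-loop system that it "could also reduce the hemodynamic impact that general anesthesia has on the patient, particularly by reducing hypotension".

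**The concern.** The outcome names attribute HR and MBP during maintenance to the drug delivery. The calculation counts minutes and does not ask what brought a value back into range. If the anesthesiologist corrects a low pressure while the controller runs, the minutes after correction count as in range, exactly as if the pressure had never needed correcting.

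These are the plan's only intraoperative hemodynamic outcomes, and they serve the secondary objective of assessing safety. A small percentage below 65 mmHg has two readings with opposite meaning for the device: it seldom lowers pressure that far, or it often does and a clinician intervenes quickly. The trial has a single arm, so no comparison group would show which reading is right.

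**Working it through.** The documents give no expected value for either outcome, so there is no figure of the plan's own to reproduce. The sample size of 139 was set without the secondary outcomes and does not depend on this point. The check is first one of reading, then an illustration.

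**Step 1: can the plan's data separate the two readings?**

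| Question | Protocol | SAP |
|---|---|---|
| Does the outcome formula use hemodynamic treatment? | No (Clinical study description) | No (Outcomes) |
| Is such treatment a listed variable? | No (Measured variables) | No (Analyses) |
| Might notes capture it? | Possibly, as an interacting drug or as a drug relevant to an objective; not named | Notes are mentioned only for malfunctions and critical issues (Data management) |
| Is there a rule for using such notes? | They are to be considered in the analysis; no method given | None; descriptive statistics only |

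For one patient, the time below the limit is 100 × (minutes below) / (maintenance minutes). Take 120 minutes of maintenance (an assumption). A fall below 65 that ends by itself after 5 minutes scores 100 × 5/120 = 4.2%. A fall that is ended by treatment at 5 minutes also scores 4.2%. Two cohorts made up of such patients would have the same mean, SD, median and IQR, and only a record of treatment would tell them apart.

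**Step 2: how far might treatment move the figure?** The documents do not give the share of patients treated, episode length, maintenance duration or interval between non-invasive pressure readings. All inputs here are assumptions.

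One episode, 15 minutes if not corrected and 5 minutes if corrected:

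| Maintenance | Not corrected | Corrected at 5 min |
|---|---|---|
| 60 min | 15/60 = 25.0% | 5/60 = 8.3% |
| 120 min | 15/120 = 12.5% | 5/120 = 4.2% |
| 180 min | 15/180 = 8.3% | 5/180 = 2.8% |

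The shift in the cohort mean is 100 × f × m / T, where f is the share of patients treated, m the minutes corrected per treated patient and T the maintenance minutes:

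- Smallest case: f = 0.10, m = 5, T = 180 gives 100 × 0.10 × 5/180 = 0.3 percentage points.
- Middle case: f = 0.30, m = 10, T = 120 gives 100 × 0.30 × 10/120 = 2.5 points.
- Largest case: f = 0.50, m = 20, T = 60 gives 100 × 0.50 × 20/60 = 16.7 points.

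These are shifts in a mean. If the Shapiro-Wilk test leads to a median and IQR, they do not carry over directly.

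**Step 3: would the missing figure be informative at this sample size?** The 95% half-width for a proportion is 1.96 × √(f(1 − f)/139). It is 5.0 points at f = 10%, 7.6 at 30% and 8.3 at 50%. The share treated could therefore be reported with useful precision without more patients.

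**The case against.** The strongest reply is that the plan already has a safeguard. Notes are kept in the report file with the time series. The concomitant-medication section exists to capture drugs that may distort the secondary measures, and the warning about forgotten entries covers any drug relevant to either objective. A drug given to change HR or MBP fits that purpose. This stands against a stronger reading that a reader might infer: that such treatment falls outside every recording provision and could never be reported. The documents do not define which drugs interact, and some use may well be noted. What remains is that the class is not named, fluids are not mentioned, entries may be missed, and the SAP does not say what to do with the notes. Even a complete note leaves the outcome calculation unchanged.

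A second reply is that the trial is pragmatic and descriptive, so HR and MBP under closed-loop anesthesia with usual care are legitimate quantities. That is right. Bias is the wrong word unless the target is what would happen without treatment. The difficulty is that the label promises an effect of drug delivery.

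A third reply concerns the hypotension benefit. A reader might infer that the plan sets out to show fewer hypotensive episodes and that missing treatment data defeats this. The documents say only that a reduction could occur. It is neither an objective nor a planned comparison, and a single arm could not establish it even with full treatment records.

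It is also fair to say that the rationale describes the anesthesiologist's role in general. That such treatment is given while the controller runs is a plausible inference, and its frequency is unknown.

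**Conclusion.** The point holds as one of definition, recording and labelling. As written, the HR and MBP outcomes describe the controller together with whatever hemodynamic management accompanies it, and a low time below 65 mmHg or below 50 bpm cannot be read as little hypotension or bradycardia.

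The size of the effect cannot be computed from the documents. The range of 0.3 to 16.7 percentage points in mean time below 65 rests wholly on assumed treatment rates, minutes corrected and maintenance durations. It shows that the effect may be negligible or large, not what it is in this trial. A treated episode is not erased either, because the minutes below the limit before correction still count.

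The outcomes are secondary and descriptive. The primary outcome and the sample size of 139 are not touched. This is a cheap improvement that changes what the safety outcomes can tell the reader.

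**What to change.** - **Record.** Make hemodynamic treatment during automatic control (drug or fluid, and time) a required annotation in the existing notes field. Add it to the variable lists in the protocol (Measured variables) and the SAP (Analyses).
- **Report.** In the SAP, give the number and percentage of patients treated beside the MBP and HR percentages. Add the percentage of patients with MBP below 65 or treated for hypotension, and the same for HR below 50 or treated for bradycardia.
- **Rename.** Call the outcomes HR and MBP during closed-loop control, including usual hemodynamic management.
- **Do not over-read.** If results are also shown for treated and untreated patients, call them descriptive. Treatment follows from low values, so the untreated group will look better by selection, and the contrast is not a controller effect.

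The cost is a little more annotation, a few table rows and possibly a less favourable hypotension figure. One should not assume that the data already exist elsewhere, because the listed contents of the anesthesiology record form include no intraoperative drugs. Parts of both documents are in the past tense. If enrolment is over, renaming is still possible, and whatever the notes contain can be reported with their completeness stated as unknown. Nothing here changes how patients are treated.
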